Study Protocol

IRB ID: 20180597 (CR00012479)

Study Number: 1 R34 DA043784-01A1

Date: July 19, 2018

Study Title

Culturally Modified Family Based Therapy for Haitian Youth in South Florida
(CIFFTA).

NCT number: 03876171

Date: July 19, 2018

INSTRUCTIONS:

1) Protocol Title

Culturally Modified Family Based Therapy for Haitian Youth in South Florida (CIFFTA).

2) IRB Review History*

None

3) Objectives*

The study will pursue the following Specific Aims:

Aim 1. To adapt CIFFTA and the assessment instruments necessary to test its efficacy to the unique Haitian sociocultural contexts. This process of adaptation has the purpose of optimizing CIFFTA's acceptability and cultural appropriateness. It will rely on ethnographic methods (participant observations, focus groups, and interviews) to guide the adaptation process.

Aim 2. Determine, via a pilot efficacy trial, the impact of CIFFTA compared with standard-of-care for reduction of drug use, risky sexual behaviors, and delinquency risk among Haitian adolescents ages 13 to 17 in Miami-Dade County. The ethnographic component of the study will monitor the delivery of the intervention, collecting process data, and affording the investigators needed perspective on the intervention's impact.

Aim 3. To generate preliminary data on the usefulness of assessment tools and CIFFTA's efficacy among the population. These data will help evaluate the effect of the intervention and its best form of implementation. They will also provide preliminary evidence to justify a full clinical trial of CIFFTA in a population of at-risk Haitian youth.

Primary study outcomes include: intervention attendance and completion; sustained abstinence in substance use through biochemical verification and self-report; family functioning; sexual risk behavior; and conduct disorder. Secondary outcomes include: recidivism in delinquency, improvement in family communication, and peer/gang involvement. Outcomes will be assessed through follow-up instruments at three points: 3, 6 and 12 months.

4) Background*

Despite preventive efforts made over the last three decades, it is clear that some populations have not benefited from attempts to deter them from risky behaviors. Haitian youth constitute an important but understudied population who may be particularly

Study Protocol

IRB ID: 20180597 (CR00012479)

Study Number: 1 R34 DA043784-01A1

Date: July 19, 2018

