school, criminal friends, alcohol/drug use, leisure/recreation, personality/behavior, family circumstances, and attitudes/orientation) yielding overall risk scores ranging from (0-8). The YLS/CMI is administered to all juveniles processed in the JSD. The same instruments will be used to assess youth from the GRP.

Drug use and psychological adjustment will be assessed with the Comprehensive Adolescent Severity Inventory developed by Myers and colleagues (52). The CASI covers a broad range of psychosocial and risk behaviors including information on substance abuse (e.g. age of first use, current patterns of use, friends' use), criminal activity, mental health, peer relationships, family/household relationships, education, and sexual behavior. Among other things, the instrument gathers information concerning youth use of a range of substances and will be adapted to assess ATOD use at baseline and post-intervention. In this way, we will be able to determine participants' historical and recent use (i.e. past 30 days, past 3, 6, and 12 months), if any, of drugs and alcohol. Similar assessments are made of sexual risk behavior and a global assessment of psychological adjustment is included that yields a continuous measure of global functioning. Adequate levels of internal consistency, test-retest reliability and validity coefficients are reported.

Conduct Disorder. Youth problem behaviors will be measured using the Conduct Disorder instrument from a Revised Behavior Problem Checklist (53) utilized previously by BSFT staff (54). The RBPC is an empirically derived measure consisting of 89 problem behaviors. We will adapt the instrument to include behaviors that are particularly salient among Haitian youths and exclude others that are deemed less salient. For each youth, the primary caregivers will rate the severity of each behavior on a 3 point scale (0 = no problem, 1 = mild problem, 2 = severe problem). The Conduct Disorder Subscale as used for this study consists of 22 items ($\alpha = .92$) measuring the youth's disruptive behavior at home (e.g., "disobedient; difficult to control"). The Conduct Disorder Subscale will be administered at intake and again at termination.

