difference at a particular time between the two conditions (6). Following Cohen's guidelines (5), we will interpret our effect sizes using the convention of "small" ( $d = .2$ ), "medium" ( $d = .5$ ), and "large" ( $d = .8$ ).

Our hypotheses concerning the direct and indirect effects of key variables on drugs/alcohol use, risky sexual behavior, delinquent behavior, and recidivism will be tested using SEM mediation analyses. To test potential indirect relationships we will include several mediators, including family connectedness, acculturation (bicultural involvement scale), and motivation to change. This will allow us to examine whether CIFFTA directly effects our outcomes of interest and/or whether the effect of CIFFTA operates through its effect on family connectedness, acculturation, and motivation to change. These mediation models will enable us to address **Specific Aim #2** by testing the significance of paths in the model linking the intervention variable to the risk-related outcomes in question (both at discrete points in time and as the change index derived from differences in ordinal frequency at baseline and at post-intervention time intervals).

In a separate set of analyses, we will examine the hazard rate of drug/alcohol use and sexual risk behavior during the post-intervention phase of the study. Comparisons across the two intervention conditions will thus be made regarding the hazard rate of having sex during the post-intervention period, sex with multiple partners ( $>1$  per month), and unprotected sexual episodes. Specifically, shared frailty Cox proportional hazard regression will be utilized to examine possible differences in the hazard rate of various risky behaviors (drug- and sex-related) in CIFFTA and control conditions during the post-intervention phase. This will prove particularly helpful in determining the hazard rate for post-intervention sexual initiation or unprotected sex in the two groups being compared, while also controlling for the time-dependence nature of our data. Similar analyses will be performed regarding initiation into drug use and other problem behaviors to determine whether the possible benefits of the CIFFTA approach extend to a range of risky behaviors.

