Survival analyses can also be performed within a SEM framework. We will utilize shared frailty proportional hazard Cox regression as it does not make assumptions about the baseline hazard rate like other survival analyses (e.g., exponential, Weibull), while the shared frailty component of the model will allow us to adjust for the dependence of survival times via random effects (12). Survival analysis is ideal for estimating time-to-event data such as the hazard rate of drug/alcohol use and sexual risk behavior during the post-intervention phase. Because our study contains 4 waves, each with their own start/finish date, the data will be right-censored, thereby necessitating the use of survival analysis techniques. While ordinary least squares regression treats censored cases as missing, survival analysis will adjust for censoring when calculating hazard rates, providing more accurate estimates (12).

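### The hazard analyses use a continuous-time shared-frailty Cox model for events known only by interview window; the frailty cluster and tie method are unstated, and a youth-level frailty would be practically inestimable for initiation

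*SAP*

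**What the plan says.** **Model.** SAP, Analytic Methods: "shared frailty Cox proportional hazard regression will be utilized to examine possible differences in the hazard rate of various risky behaviors". The outcomes are mixed. Some can happen only once per youth: the SAP refers to the "hazard rate for post-intervention sexual initiation or unprotected sex in the two groups being compared" and adds "Similar analyses will be performed regarding initiation into drug use and other problem behaviors". Others can recur, such as multiple partners "and unprotected sexual episodes".

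**Frailty and censoring.** SAP, Analysis Rationale: "the shared frailty component of the model will allow us to adjust for the dependence of survival times via random effects". The unit that shares the frailty (youth, family, therapist or wave) is not named. On censoring it says "Because our study contains 4 waves, each with their own start/finish date, the data will be right-censored". Grouped times, interval censoring and ties are not mentioned.

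**Data.** Protocol section 3: "Outcomes will be assessed through follow-up instruments at three points: 3, 6 and 12 months". Section 10 (Overview of Assessment Procedures and Attrition) counts these from the end of the intervention. Under Instrumentation in section 10, the drug-use instrument gives "historical and recent use (i.e. past 30 days, past 3, 6, and 12 months", and sexual risk is assessed in a similar way. Age of first use is also collected, but neither document plans event dates for these behaviours.

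**Conflicting schedule.** Protocol section 8 lists intake, outtake, a booster session three months later and a final assessment at 12 months. That could leave a single follow-up window.

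**The concern.** A Cox model orders events by time. Here a first event is known only to lie between two interviews, or within a recall window, so many youths share the same recorded time. The estimate then depends on how ties are handled, and the SAP does not say.

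The frailty raises a separate question. A shared frailty is learned from several event times within the same cluster. For sexual or drug-use initiation each youth contributes at most one, so a youth-level frailty has no within-youth dependence to absorb. Its variance would come from elsewhere in the model, and the hazard ratio moves with it.

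This matters because the SAP intends the pilot to supply effect sizes for a possible full trial.

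**Working it through.** **Stated figures.** The documents give no event rate, hazard ratio or power for the hazard analyses, so there is no figure to reproduce. The stated power of 0.84 to 0.86 concerns the SEM.

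**Inputs.** From the documents: 80 analysed, 1:1 allocation (40 per arm), interviews at 3, 6 and 12 months, four waves. Assumed: true hazard ratio 0.5 (log HR -0.693), exponential times, 12-month control risk 0.3, 0.5 or 0.8, two-sided 5% tests, and all 80 youths at risk (an upper bound for initiation).

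**Step 1. Grouping.** Event times were simulated (300 to 400 replicates), grouped at 3, 6 and 12 months and analysed four ways. Mean log HR:

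| Control risk | Exact-time Cox | Breslow | Efron | Complementary log-log |
|---|---|---|---|---|
| 0.3 | -0.731 | -0.700 | -0.730 | -0.736 |
| 0.5 | -0.760 | -0.696 | -0.758 | -0.767 |
| 0.8 | -0.713 | -0.584 | -0.703 | -0.724 |

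Shrinkage = 1 - (grouped log HR / exact-time log HR).
- Breslow: 1 - 0.700/0.731 = 4%; 1 - 0.696/0.760 = 8%; 1 - 0.584/0.713 = 18%.
- Efron: largest is 1 - 0.703/0.713 = 1.4%.
- Complementary log-log: within 1.5% of exact-time Cox. Power 0.30, 0.53 and 0.72, against 0.29, 0.53 and 0.71.

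Two variations:
- Seven windows, with recall periods used to split the intervals: Breslow shrinkage is 1 - 0.665/0.691 = 4% at risk 0.5 and 1 - 0.615/0.676 = 9% at risk 0.8.
- One 12-month window, risk 0.8: Breslow 1 - 0.376/0.698 = 46%; Efron 1 - 0.622/0.698 = 11%.

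**Step 2. Youth-level frailty with one event per youth.** For a gamma frailty with mean 1 and variance θ, survival is S = (1 + θHe^(βx))^(-1/θ), where H is the cumulative baseline hazard.
- Without covariates, three windows give three free probabilities and three hazards, so every θ fits equally well. The maximised log-likelihood was -106.323668 for θ = 0, 0.5, 1, 2 and 4.
- With arm there are 2 × 3 = 6 free probabilities and 3 + 1 = 4 parameters before θ. The two spare degrees of freedom measure departure from proportional hazards, and θ is estimated only from those.
- With one window there are 2 free probabilities and 2 parameters, so nothing is left for θ. Then HR = (S1^(-θ) - 1)/(S0^(-θ) - 1). With S0 = 0.5 and S1 = √0.5 = 0.707, θ = 1 gives 0.414/1 = 0.41 and θ = 2 gives 1/3 = 0.33. At θ = 0 it is 0.50. The data cannot choose between them.

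With three windows and a true θ of 0, imposing θ = 2 gives:

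| Control risk | Loss in 2 × log-likelihood | HR (true 0.50) |
|---|---|---|
| 0.3 | 0.04 | 0.42 |
| 0.5 | 0.23 | 0.37 |
| 0.8 | 1.30 | 0.31 |

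All three losses are far below 3.84, so the data would not reject θ = 2.

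In simulation (risks 0.5 and 0.8, true θ of 0 or 1, 100 replicates each), the 95% likelihood-ratio set for θ covered the whole grid from 0 to 8 in 48 to 88% of trials. A true θ of 1 was detected in 2 to 5%, no better than the false detection rate of 0 to 7% when θ was 0. When θ was estimated and the truth was no frailty, the mean log HR moved to about -1.0 to -1.2 and its root mean squared error roughly doubled. The exact size depends on how large θ is allowed to become.

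**Step 3. Wave as the cluster.** 88/22 = 4 waves, so the frailty variance would rest on four clusters.

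**The case against.** **Cox is usable here.** With Efron ties and three windows the bias is about 1%, and the SAP does not choose Breslow. This stands. A reader might infer that Cox is invalid for these data or that the hazard ratio will be badly biased. The documents do not support that: material loss needs Breslow ties with high event risk, or a single window.

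**The SAP does not state a youth-level frailty.** This also stands. A reader might infer that the SAP plans a frailty that is not identified. The cluster is unnamed, and strict non-identification holds only without covariates or with a single window. With arm and three windows the variance is weakly identified. For recurrent behaviours a youth effect is meaningful.

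**Times may be finer than three values.** Recall windows, age of first use and the SAP's per-month definition of multiple partners could split intervals. The questionnaire items are not shown, so three distinct times is not established. Seven windows still left 4 to 9% shrinkage under Breslow.

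**The replacement overstates the effect.** Complementary log-log means (-0.736, -0.767, -0.724) do exceed -0.693 in size, but exact-time Cox on the same data gives -0.731, -0.760 and -0.713. The excess is small-sample bias and simulation error (standard error about 0.015 to 0.03), not a fault of the model. Adding wave fixed effects does cost something. In a separate simulation at risk 0.3 the root mean squared error was 0.54, against 0.53 for Efron Cox. That version fits seven parameters (three intervals, arm, three wave contrasts) to about 40 × 0.30 + 40 × (1 - √0.70) = 12 + 6.5, or about 19 events.

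**Low stakes.** The main efficacy analysis is latent growth modelling, and the SAP calls its analyses preliminary. This stands and limits the weight of the point.

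**Conclusion.** The concern holds in limited form. The planned model assumes near-continuous event times and recognises only right-censoring, while the data are grouped by interview and recall window. How much this matters depends on the unstated tie method: about 4 to 18% shrinkage of the log HR under Breslow with three windows and about 1% at most under Efron. With one 12-month window at control risk 0.8 the figures are 46% and 11%.

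The frailty is the more consequential half. The cluster must be named. If it is the youth, the initiation hazard ratio would depend on a variance that 80 youths cannot inform, and estimating it can exaggerate the effect and roughly double its error. If it is the wave, four clusters are too few to estimate a variance well.

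The sizes rest on assumed control risks of 0.3 to 0.8, a hazard ratio of 0.5, exponential times and all 80 youths at risk. Fewer youths at risk of initiation would leave still less information on the frailty. The impact on the trial is modest, because these are separate and preliminary analyses.

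**What to change.** - Use a discrete-time proportional hazards model (complementary log-log link) with one indicator per assessment interval and a term for arm. It leaves the baseline hazard free, as the SAP wants, and the arm coefficient is still a log hazard ratio. If Cox is kept, specify Efron ties at minimum.
- Fit no youth-level frailty for initiation. Restrict the initiation risk set to youths who have not yet initiated at the time origin, and state that origin.
- Use a youth random effect only for behaviours that can recur across intervals, and name the cluster wherever a random effect is used.
- Treat wave fixed effects as optional, given the few events expected.
- Reconcile the assessment schedules in Protocol sections 3, 8 and 10, which set the number of intervals.

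Cost: some SAP wording and a few interval parameters, with precision about equal to exact-time Cox. This is a cheap improvement.

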This is a multi-wave study, with approximately all the participants recruited by the end of Year 02 and the remainder in the beginning of Year 03. At baseline, we will conduct comprehensive assessments of all study constructs and repeat all other assessments annually. Activities during the first three months will consist of the following: Staffing, Instrument Calibration, Ethnographic Update. Each wave will be composed of 22 participants to be randomized into two groups (11 each). Each undergo assessment at intake (T1) and outtake (T2), a booster session 3 months after outtake and a final assessment at 12 months. Data analysis process will be initiated at the third month and continue throughout the study implementation.

Study Protocol

[figure not shown]
IRB ID: 20180597 (CR00012479)

Study Number: 1 R34 DA043784-01A1

Date: July 19, 2018

Publications are expected to start from month 20. The table below details the activity processes.

Project Timeline

9) Study Endpoints*

Primary outcomes are: intervention attendance and completion; sustained abstinence in substance use through biochemical verification and self-report; family functioning; sexual risk behavior; and conduct disorder.

Secondary outcomes include recidivism in delinquency, improvement in family communication, and peer/gang involvement.

10) Procedures Involved*

RCT procedures

CIFFTA has three major components – Family-Based Therapy, Individual Therapy, and Psycho-educational Modules – delivered over 16 weeks in a six sessions (60 minutes each) per month format. In this study, the therapy will be delivered in the home to reduce missed sessions and premature termination. Special training will focus on how to structure the home environment to reduce distractions. Three sessions per month will typically be a session which may include Family-based Therapy or Psycho-educational modules with the family or parents alone (e.g., parent training). The other three sessions are typically with the adolescent alone and include Motivational Interviewing or Psycho-educational modules designed for the adolescent.

Study Protocol

IRB ID: 20180597 (CR00012479)

Study Number: 1 R34 DA043784-01A1

Date: July 19, 2018

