& Wilson, 1998), they are minimally invasive, can be collected in the community during follow-up assessments and carry fewer taboos on collection (Meyers et al., 2002). Urine screen results will be kept confidential in containers marked with pre-printed labels without personal identifying information. To assure integrity of the sample, the Onsite CupKit® automatically checks for temperature, and the interviewer will ensure that there is no one else in the restroom.

Study Protocol

IRB ID: 20180597 (CR00012479)

Study Number: 1 R34 DA043784-01A1

Date: July 19, 2018

12) Data Management*

Qualitative data:

Research staff will be monitored during every step of data collection by appropriate investigators. Instruments will be reviewed periodically to insure validity and reliability. Data will be entered by our personnel into a database under the supervision of PI. Control measures will be instituted to ensure accuracy of data entry procedures prior to analysis. Also, all data will be analyzed at our data processing center, under guidelines of our data safety and monitoring plan. All written and tape-recorded materials in this study will be transcribed using Microsoft Word on a daily basis and stored in locked the PI files cabinet. They will be coded and analyzed using procedures described in Schensul et. al.

The PI, with the assistance of the project's co-Is and Post-Doctoral Associate, will analyze the data using SPSS®, STATA®, the R statistical package or relate statistical software. Outcome measures will include drug use, delinquency/crime, family functioning, educational performance, and emotional/ psychological functioning. Predictor and outcome data will be analyzed using confirmatory factor analysis, generalized linear mixed effects modeling, latent growth modeling, structural equation modeling, analysis of variance, logistic regression, and stepwise multiple regression. The significance levels will be adjusted to control for multiple outcome measures. For the primary hypotheses, power is anticipated to be .80.

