### ***Analytic Methods***

Latent Growth Modeling within a Structural Equation Model (SEM) framework. We will conduct latent growth curve analyses using Stata 14 gsem (1), SAS Proc Mixed (2), SPSS Mixed Models, and/or Mplus 8 (3) to compare the trajectories of participants in CIFFTA to those in TAU. Given that the data are balanced and have more than 2 time points, the model is identified, thereby allowing us to perform SEM growth curve analysis (4). These models conceptualize each component of growth (the baseline/intercept, the slope/rate of change, the quadratic slope, etc.) as composed of a fixed and random effect. Thus, these models have multiple components of variance as well as a regression-type model of the underlying mean growth curves of the two groups. Within an SEM framework, growth curves are treated as latent (unobserved) variables influenced by occasion- and individual-level covariates, allowing us to explicitly model growth trajectories overtime.

Specific analysis link functions will be matched to fit the distribution of each outcome variable. For ordinal outcomes (e.g., frequency of drug/alcohol usage), we will use an ordinal logistic regression function. The proportional odds assumption will be evaluated using the Brant test, and if needed, addressed by allowing problematic coefficients to vary across levels of the outcome variable. Count outcome measures (e.g., number of sexual partners, problem behaviors, re-arrests) will be analyzed using a negative binomial function rather than Poisson regression to address potential over-dispersion. Vuong tests will be performed to assess whether the data have an excess of zeros, and if necessary, zero inflated negative binomial regression will be used instead.

Analysis for Aims 2 and 3: The first set of analyses will explore the efficacy of CIFFTA compared to SOC in modifying the main adolescent outcomes and to generate effect sizes for a possible full clinical trial: a) drug/alcohol use, b) risky sexual behavior, c) delinquent behavior, and d) recidivism. Latent growth modeling will be used to investigate the efficacy of CIFFTA as compared to SOC. For each model, we will examine the effect sizes to determine the overall impact of CIFFTA over SOC on the outcome variables. We will generate estimates of effect sizes, such as Cohen's d (5), for both rate of change and for the

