**Power Analysis:** We will recruit 88 participants for this study, with the intention of analyzing data for 80 participants after attrition. The original CIFFTA randomized trial with 28 Hispanic adolescents showed CIFFTA to be more efficacious than the comparison family treatment at: 1) reducing drug use, and 2) improving parenting practices as reported by adolescents (7). More recently, a technology assisted CIFFTA study of 80 minority youth at high risk for drug use showed CIFFTA to be more efficacious in reducing behavior and conduct problems and in improving family cohesion, when compared to a delay treatment condition (8). Based on these findings, CIFFTA was placed on the National Registry of Evidence Based Practices using their more rigorous criteria for entry. Given such consistent findings of efficacy for CIFFTA among Hispanic youth, a sample size of 80 will be sufficiently powerful to detect relatively small effects ( $R^2 = 0.05$ ) at adequate levels of power (0.84 - 0.86) using a relatively simple SEM. A sample size of 80 is also well above sample guidelines for Stage 1 treatment trials (80)). Nevertheless, to deal with attrition, which in the case of Haitian and because of the ethnographer's engagement with the families will not be higher than 10%, we plan a sample of 88 adolescents.

Nevertheless, we recognize and appreciate the limits of estimating simple SEMs, such as ours, with a small sample size. Therefore, we will take several steps to mitigate concerns about statistical power, including: limiting the use of latent variables when possible, constructing parsimonious path models, and using Bayesian estimators. When theoretically and empirically appropriate, we will use principal components factor analysis to combine multiple indicators into a single scale capturing the underlying construct rather than estimating multiple latent variables since the latter often requires larger samples.

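### The SAP calls R² = 0.05 relatively small, but read as the two-arm contrast it is d = 0.46, near the SAP's own medium; power for its small effect (d = .2) is low

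*SAP*

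**What the plan says.** The SAP's Power Analysis plans 88 recruits "with the intention of analyzing data for 80 participants after attrition". It then claims that "a sample size of 80 will be sufficiently powerful to detect relatively small effects ( $R^2 = 0.05", and puts this "at adequate levels of power (0.84 - 0.86) using a relatively simple SEM". It gives no alpha, no sidedness, no model and no correlation between repeated measures. It does not say which path or set of predictors the R² refers to.

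Results are to be reported on a different scale. Under Analysis for Aims 2 and 3 the SAP says: "We will generate estimates of effect sizes, such as Cohen's d (5), for both rate of change and for the" difference between conditions at a given time. It adds that "we will interpret our effect sizes using the convention of 'small' ( $d = .2$ ), 'medium' ( $d = .5$ ), and 'large' ( $d = .8". R² = 0.05 is not translated to this scale anywhere, and no power is given for any value of d.

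Three other statements bear on the point:

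- Protocol section 8 fixes 1:1 allocation: "Each wave will be composed of 22 participants to be randomized into two groups (11 each".
- Protocol section 12 anticipates power of .80 for the primary hypotheses without naming an effect size, and says: "The significance levels will be adjusted to control for multiple outcome measures".
- The SAP's Power Analysis goes on to acknowledge the limits of a small sample and to call the analyses preliminary, but it does not withdraw or qualify the sensitivity claim.

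**The concern.** The SAP uses two effect-size scales without linking them. A reader who meets the claim about relatively small effects will apply the only numerical definition of small that the SAP gives, d = .2. For a balanced two-arm contrast, R² = 0.05 is more than twice that and close to the SAP's medium.

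This matters because the pilot's main product is a set of d values for planning a full trial and supporting a larger grant application. Those estimates will be read against the stated sensitivity. If small effects are believed to have been detectable, a non-significant d of about .2 or .3 invites the inference that nothing worthwhile is there, although the design would often miss a true effect near .2. That could end development too early or distort the size of the next trial.

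**Working it through.** **Inputs.** Analysed N = 80, R² = 0.05, power 0.84 to 0.86 (SAP, Power Analysis). Allocation 1:1, so n = 40 per arm (Protocol section 8). Small d = .2, medium d = .5 (SAP, Analysis for Aims 2 and 3). Assumed, because not stated: two-sided alpha 0.05, with one-sided 0.05 as a variant.

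**1. Conversion, if R² is the arm contrast.** R² = d²/(d² + 4), so d = 2√(R²/(1 − R²)).

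- R² = 0.05: d = 2√(0.05/0.95) = 2√0.0526 = 0.459. This is 0.459/0.5 = 92% of medium and 0.459/0.2 = 2.3 times small.
- d = .2: R² = 0.04/4.04 = 0.0099, about one fifth of the R² used.
- d = .5: R² = 0.25/4.25 = 0.0588.

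**2. The plan's own power figure.** For a plain two-arm test, δ = d√(n/2) = 0.459 × √20 = 2.052.

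- Two-sided 0.05: Φ(2.052 − 1.960) = 0.537; the exact t gives 0.527.
- One-sided 0.05: Φ(2.052 − 1.645) = 0.658.
- Power of 0.84 to 0.86 (two-sided) needs δ = 1.960 + 0.994 = 2.954 to 1.960 + 1.080 = 3.040. The residual variance must then fall to (2.052/2.954)² = 0.48, or (2.052/3.040)² = 0.46, of its value: a cut of 52 to 54%. A baseline covariate correlated √0.52 = 0.72 to √0.54 = 0.74 with the outcome would do this, and so could several averaged follow-ups.

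A plain test therefore does not reproduce 0.84 to 0.86. The figure is attainable with a precision gain that the SAP does not specify.

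**3. Power at d = .2.**

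| Basis | Two-sided 0.05 | One-sided 0.05 |
|---|---|---|
| Plain two-arm test, 40 per arm | 0.14 | 0.22 to 0.23 |
| SAP's 0.84 to 0.86 accepted at d = 0.459 | 0.25 to 0.26 | 0.31 to 0.33 |

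The plain figure is Φ(0.2 × √20 − 1.960) = Φ(−1.066) = 0.143. The second row scales δ by 0.2/0.459: Φ(2.954 × 0.436 − 1.960) = 0.251 and Φ(3.040 × 0.436 − 1.960) = 0.263. The same scaling at one-sided 0.05 gives 0.311 and 0.324; an F test at two-sided 0.10 gives up to 0.33.

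**4. If R² is instead a partial R²** after covariates explaining a share v of the outcome variance, the d in raw SD units is 0.459√(1 − v).

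- v = 0.25: d = 0.397. v = 0.50: d = 0.324. These are 2.0 and 1.6 times small.
- Power at d = .2 from the covariate gain alone, two-sided: Φ(0.2√(20/0.75) − 1.960) = 0.18 and Φ(0.2√(20/0.50) − 1.960) = 0.24.
- If 0.84 to 0.86 is also accepted at these smaller effects, δ scales by 0.2/0.397 or 0.2/0.324. Power at d = .2 is then 0.32 to 0.33 or 0.45 to 0.47, two-sided. The most favourable case, one-sided with v = 0.50 and 0.86, is Φ(2.725 × 0.2/0.324 − 1.645) = 0.51.

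**5. Effect detectable with 0.80 power.**

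- Plain test, two-sided: (1.960 + 0.842)/√20 = 0.627; the exact t gives 0.634. This is R² of about 0.09, between the SAP's medium and large.
- SAP's power accepted at d = 0.459: 0.459 × 2.802/2.954 = 0.435 to 0.459 × 2.802/3.040 = 0.423.
- In the plain test an observed d below 1.991/√20 = 0.445 is non-significant.

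**The case against.** The strongest reply is that the SAP never ties its R² to the arm contrast. It refers only to a relatively simple SEM, and the planned models include mediated paths and growth curves. Several outcomes are ordinal, count or time-to-event, for which a normal-theory d is only an approximation. This stands. It makes d = 0.46 conditional and is why the partial R² range is shown. It does not rescue the sentence: if the R² belongs to some other path, the SAP gives no sensitivity at all for the comparison in Aim 2.

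A second reply is that relatively small is a loose phrase with the exact R² printed beside it, and that the SAP calls the work exploratory and preliminary. That lowers the stakes, but it leaves the stated sensitivity uncorrected on the scale used for reporting.

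A reader might also infer several stronger things that the documents do not support:

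- *That 0.26 is a ceiling on power at d = .2.* It depends on two-sided 0.05 and on R² being the raw arm contrast. Other readings give higher values, up to 0.51. The multiplicity adjustment promised in the Protocol would lower all of them.
- *That 0.84 to 0.86 is wrong.* Repeated measures or baseline adjustment could supply the gain. The inputs are missing, so the figure can be neither confirmed nor refuted.
- *That the SAP claims power for d = .2, or will treat non-significance as no effect.* It says neither. The risk lies in how its wording may be read.
- *That effects across .2 to .4 are out of reach.* If the SAP's power is accepted at d = 0.459, d = .4 has power Φ(2.954 × 0.4/0.459 − 1.960) = 0.73, or 0.76 from 3.040. The problem is greatest near .2.

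**Conclusion.** The point holds in conditional form. If the R² is the variance explained by the 1:1 arm contrast, the effect the SAP calls relatively small is d = 0.46, near its own medium. On the partial R² reading it is about 0.40 to 0.32, still clearly above its small.

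With 40 per arm and two-sided 0.05, power at d = .2 is about 0.14 in a plain test and 0.25 to 0.26 if the SAP's power is accepted at d = 0.46. One-sided, the figures are about 0.23 and 0.31 to 0.33. Combining the partial R² reading with acceptance of the SAP's power raises this, but even the most favourable case is about one half, well short of 0.80. These results assume N = 80, equal arms, an approximately normal outcome and no multiplicity adjustment.

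This is a fault in how sensitivity is described. It does not show that the pilot is too small for its stated preliminary purpose.

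**What to change.** In the SAP's Power Analysis:

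1. Replace the relatively small label with the effect on the reporting scale: about d = 0.46, near medium, if R² = 0.05 is the arm contrast. Name the path, the alpha and sidedness, and the model. If R² is a partial or multi-predictor quantity, say so and give the corresponding d.
2. Do not simply attach 0.84 to 0.86 to d = 0.46. Either give the repeated-measures or baseline-correlation assumptions that produce it, or restate the power for a plain two-arm test: about 0.53 at d = 0.46, with 0.80 reached at d of about 0.63.
3. State that effects near d = .2 are not reliably detectable with 80 participants. Quote each power figure with its own assumptions; 0.14 and 0.26 rest on different precision and should not be merged into one range.
4. Commit to reporting arm effects with confidence intervals, so that a non-significant result is not read as absence of a small effect.

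The cost is SAP wording and a less favourable stated sensitivity. Sample size and conduct do not change.
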